The estimand for the primary analysis will use the Treatment Policy Strategy for most intercurrent events; selected intercurrent events leading to data that are missing completely at random may be addressed with a While-on-Treatment Strategy (e.g., if site closures due to coronavirus disease 2019 [COVID-19]).

The number of subjects treated, the number of doses administered and the reason for discontinuing treatment will be summarized, along with demographic and Baseline characteristics.

The primary efficacy endpoint is the proportion of responders during Month 6. The proportion of time each subject's sUA is <6 mg/dL will be calculated using observed data at Weeks 20, 21, 22, 23 and 24. The amount of time that sUA is <6 mg/dL (using linear interpolation, if necessary) will be calculated and divided by the total amount of time from the first to the last observed sUA value in this time range (missed values in this time range will be ignored for purposes of this calculation). Subjects who have no available sUA value in this time range will be imputed as non-responders unless the data are missing completely at random, in which case they will be omitted from the analysis. Two-sided exact 95% confidence intervals (CIs) will be calculated.

The primary analysis will be performed on all enrolled subjects who receive ≥ 1 dose of pegloticase.

The proportion of Month 3 responders will be summarized similarly to the Month 6 responders. All sUA results collected between infusions from Week 10 through Week 14 of the trial will be used in the calculation of the Month 3 responders.

The mean change from Baseline in urate deposition volume (measured by DECT) to Week 24 will be summarized along with the corresponding 95% CI for subjects with DECT assessments.

The proportion of subjects experiencing any of the following events: IR leading to discontinuation of treatment, anaphylaxis or meeting Individual Subject sUA Discontinuation Criteria will be presented. For this composite endpoint, each individual component of the composite will be analyzed with a summary of the incidence and the corresponding 95% CI.

The primary and secondary endpoints will be summarized overall and by cohort. If Cohort 2 enrolls both subjects with previous mild IR and those with no previous IR, then the data will be summarized by IR category (no IR,

mild IR) within Cohort 2 and for Cohorts 1 and 2 combined. No adjustments to CIs will be made for multiple endpoints or multiple time points.

CCI

The number and percentage of subjects with at least 1 AE, at least 1 SAE, at least 1 severe AE and with an AE that leads to discontinuation of pegloticase and/or MTX will be summarized. Adverse events will be listed.

The impact of CCI [REDACTED], efficacy (responder rate) and safety (IR) will be explored.

Sample Size Estimate:

A sample size of 30 subjects is planned for this trial to provide a sizeable number of subjects to support the following projections. The primary efficacy endpoint will be demonstrated to be statistically greater than 20% if at least 12/30 (40%) responders are observed. In that case, the lower bound of a 95% CI for the proportion of responders will be approximately 23%.

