- The adverse event (AE)/serious adverse event (SAE) profile overall for pegloticase and MTX and the incidence of adverse events of special interest (AESIs), including IRs, anaphylaxis, gout flares and major adverse cardiovascular events (MACE, defined as non-fatal stroke, non-fatal myocardial infarction, cardiovascular death and congestive heart failure).
- The change from Baseline in safety laboratory test results, including high-sensitivity C-reactive protein (hs-CRP).
- The change from Baseline in vital signs.

Trial Design

This is a Phase 4, multicenter, open-label trial of pegloticase with MTX in adult subjects with uncontrolled gout who were previously treated with pegloticase without a concomitant immunomodulator and stopped pegloticase due to failure to maintain sUA response and/or a clinically mild IR. Approximately 30 subjects will be enrolled. Pegloticase + MTX will be administered for approximately 24 weeks, with an optional extension up to 48 weeks.

The trial design will include 5 distinct components:

- 1) a Screening Period, lasting up to 42 days;
- 2) a 6-week MTX Tolerability Assessment Period (hereafter referred to as the MTX Run-in Period);
- 3) a 24-week Pegloticase + MTX Treatment Period, which will include a Week 24/End of Trial/Early Termination Visit (subjects that end MTX and pegloticase treatment prior to the Week 24 will remain on trial for follow up until the Week 24 visit);
- 4) an Optional Pegloticase + MTX Extension Period from Week 24 to Week 48, if a subject may gain further benefit with additional pegloticase treatment per the discretion of the Principal Investigator, which will include a Week 48/Optional End of Trial/Optional Early Termination Visit and
- 5) a 30-Day Post-Treatment Follow-up (Phone/Email) 30 days after the last pegloticase infusion or last dose of MTX (for subjects who are unable to tolerate MTX during the MTX Run-in Period and do not dose pegloticase). Subjects that end MTX and pegloticase treatment prior to Week 24 and remain on trial for at least 30 days prior to Week 24 will complete the 30-Day Post-Treatment Follow-Up as part of the visits following the End of Pegloticase visit.

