MTX for SC injection in auto-injectors (7.5, 10, 15, 20, 25 mg) will be provided to all subjects (see [RASUVO Full Prescribing Information](#)). For each subject, the MTX dose will be based on their Baseline eGFR value.

Duration of Treatment and Follow-up:

Screening. Up to 42 days prior to the Pegloticase + MTX Treatment Period.

MTX Run-in Period (Week -6 to Day 1). 6 weeks (6 doses) of MTX dosing prior to initial pegloticase dose.

Pegloticase + MTX Treatment Period (Day 1 through Week 24). 22 weeks (infusion visits every 2 weeks/12 infusions) plus the End of Trial (Week 24)/Early Termination Visit.

End of Pegloticase Visit (if applicable). If the subject discontinues pegloticase treatment prior to Week 22, such as due to the sUA Discontinuation Criteria, the subject will complete this visit within approximately 2 weeks of the last infusion. Subjects will continue on trial without infusion for the remainder of trial visits, including the 30-Day Post-Treatment Follow-up and Week 24/End of Trial/Early Termination Visits. For subjects who agree to continue trial visits after the End of Pegloticase Visit, the 30-Day Post-Treatment Follow-up Visit will be captured as part of the continued visits; however, if the last trial visit is <30 days posttreatment, the 30-Day Post-Treatment Follow-up phone call/email will still be required.

Optional Pegloticase + MTX Extension Period (Week 24 through Week 48). For subjects who may gain further benefit with additional pegloticase treatment beyond 12 infusions based on the Principal Investigator's judgement, an Optional Pegloticase + MTX Extension Period, from Week 24 to Week 48, can be added.

30-Day Post-Treatment Follow-up Visit (30 days post last pegloticase infusion). All subjects will receive a safety follow-up phone call/e-mail/visit approximately 30 days after the last dose of MTX or the final infusion of pegloticase, whichever occurs last. Subjects who receive at least 1 dose of MTX and are females of childbearing potential, will receive a safety follow-up phone call/e-mail approximately 4 weeks/30 days after the last dose of MTX to verify at least 1 ovulatory cycle has occurred after the last dose of MTX. If the subject has not ovulated, a urine pregnancy test will be performed.

MTX Partner Pregnancy Follow-up. Subjects who receive at least 1 dose of MTX and are non-vasectomized males will receive a phone call/e-mail inquiry 3 months after MTX discontinuation regarding partner pregnancy.

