11. AEs/SAEs will be collected from the signing of the informed consent form until the 30-Day Post-Treatment Follow-up Visit. For each AE, the Investigator will be asked to record if the event was possibly an IR or anaphylaxis and if so, will be prompted to complete additional electronic case report forms. Females of childbearing potential will be asked to confirm if ovulation has occurred since the last dose of MTX. If the subject had not ovulated, a urine pregnancy test will be required.
12. The initial DECT scan will be performed after the Screening Visit, during the MTX Run-in Period and prior to the Day 1 Visit. Subsequent DECT scans may be performed ± 10 days from the scheduled visit date. Subjects who end pegloticase infusions prior to Week 24 should follow the scheduled time points and have a DECT scan at the End of Pegloticase (if applicable) and Week 24/End of Trial/ET Visits (detailed guidance is provided within the Imaging Manual). DECT will be carried out for all subjects where the site has the capability to conduct the test.
13. MTX will be dispensed and brought back to check compliance at each infusion visit. MTX should be injected 1 to 3 days prior to each pegloticase infusion; however, if a subject does not do so, MTX must be injected ≥ 60 minutes prior to each pegloticase infusion.

14. Subjects will take folic acid at a starting dose of 1 mg orally every day beginning Week -6 (preferably 2 days prior to the first dose of MTX) continuing until prior to the End of Pegloticase (if applicable) or until 1 week after the last pegloticase infusion for subjects who have not stopped pegloticase treatment. The folic acid dose can be increased or an alternative folate supplement can be used (see [Section 9.4.6.3.2.2](#) for detailed instructions).
15. Before a subject begins the Pegloticase + MTX Treatment Period, he or she must have been taking at least 1 standard gout flare prophylaxis regimen (i.e., colchicine and/or NSAIDs and/or low-dose prednisone \leq 10 mg/day) per protocol for \geq 1 week before the first dose of pegloticase and continue flare prophylaxis for at least 6 months per American College of Rheumatology guidelines ([FitzGerald et al, 2020](#)). Gout flare prophylaxis from Week 26 to the end of the trial will be administered, if needed, at the discretion of the Principal Investigator.

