 - IR prophylaxis compliance;
 - Folic acid compliance;
 - Pegloticase infusion;
 - **CCI** [REDACTED];
 - Pre-infusion **CCI** [REDACTED] sampling; and
 - MTX drug/dispensation related items.
- Re-introduction of oral urate-lowering therapies should not start until after the Week 24 or 48/End of Trial/Early Termination Visit (or End of Pegloticase Visit [if applicable]) laboratory tests are collected.

If a subject discontinues treatment or discontinues the trial prior to the 6th infusion, their available data will be included in the safety assessment conducted by the Safety Review Team.

Subjects who elect to receive pegloticase + MTX during the Optional Pegloticase + MTX Extension Period will complete the 30-Day Post-Treatment Follow-up after the final pegloticase infusion but are not required to return for biweekly visits.

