Thirty (30) days after the last MTX dose or pegloticase infusion (whichever is later), subjects will be contacted by telephone or email to review AEs, SAEs and concomitant medications. Subjects who receive at least 1 dose of MTX and are females of childbearing potential, will receive a safety follow-up phone call/e-mail approximately 4 weeks/30 days after the last dose of MTX to verify at least 1 ovulatory cycle has occurred after the last dose of MTX. If the subject has not ovulated, the subject will be requested to return to the site for a urine pregnancy test.

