9.6.7 Safety Analysis

Treatment-emergent AEs (TEAEs) during the MTX Run-in Period are defined as events with an onset date on or after the first dose of MTX through the first pegloticase infusion, or 30 days after the last dose of MTX for subjects who do not receive pegloticase. TEAEs during the Pegloticase + MTX Periods are defined as events that occur after the start of the first pegloticase infusion through 30 days after the last dose of pegloticase and/or MTX (whichever is later).

TEAEs will be summarized separately for the Run-in Period and the Pegloticase + MTX Treatment Period (inclusive of the Optional Pegloticase + MTX Extension Period). TEAEs in the Pegloticase + MTX Treatment Period will be summarized overall and by cohort. If Cohort 2 enrolls both subjects with previous mild IR and those with no previous IR, then the data will be summarized by IR category (no IR, mild IR) within Cohort 2 and for Cohorts 1 and 2 combined. AEs that occur more than 30 days after the last dose of pegloticase and/or MTX through the 30-Day Post-Treatment Follow-up Visit will also be summarized.

The number and percentage of subjects with at least 1 AE, at least 1 SAE, at least 1 severe AE and with an AE that leads to discontinuation of pegloticase and/or MTX will be summarized. Adverse events will be listed.

The number and percentage of subjects experiencing AEs will be summarized by system organ class and preferred term. Summaries by maximum severity and relationship to MTX and/or pegloticase will also be provided. SAEs and AEs leading to discontinuation of MTX and/or pegloticase will be presented by system organ class and preferred term.

The proportion of subjects with SAEs and each AESI will also be summarized.

Laboratory test results will be summarized by trial visit and change from Baseline. Shift tables for laboratory parameters by Common Terminology Criteria for Adverse Events grade will be presented. Laboratory test results will also be classified relative to the normal reference range (normal, low or high).

Vital signs, including blood pressure, respiratory rate, temperature and heart rate, will be summarized by trial visit and change from Baseline.

Prior and concomitant medications will be summarized and/or included in the data listings.

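### The 30-day safety contact that ends AE collection has two anchors; under the infusion-based one, collection for completers stops nominally 4 to 7 days before the TEAE window closes

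*Protocol*

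**What the plan says.** Contact counted from the last infusion, for anyone who received pegloticase:

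- Protocol Synopsis, Duration of Treatment and Follow-up, heading: "30-Day Post-Treatment Follow-up Visit (30 days post last pegloticase infusion").
- Protocol Synopsis (Trial Design), Protocol 9.1 and SAP 4, fifth design component: "30 days after the last pegloticase infusion or last dose of MTX (for subjects who are unable to tolerate MTX" during the run-in and never receive pegloticase). The MTX date is reserved for that never-infused group.

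Contact counted from the later of the two drugs:

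- The sentence under the Synopsis heading above: "approximately 30 days after the last dose of MTX or the final infusion of pegloticase, whichever occurs last".
- Schedule of Assessments footnote 25 and Protocol 9.5.8.7: "Thirty (30) days after the last MTX dose or pegloticase infusion (whichever is later").

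Places that do not settle it:

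- The Schedule's column header for this visit names both drugs, with a window of ±3 days, but does not say which governs.
- Protocol 9.3.3.1.1 says that extension subjects "will complete the 30-Day Post-Treatment Follow-up after the final pegloticase infusion", without a day count.

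What depends on the contact:

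- Schedule footnote 11: "AEs/SAEs will be collected from the signing of the informed consent form until the 30-Day Post-Treatment Follow-up Visit". Protocol 9.5.4.1.2 says the same.
- The TEAE window in Protocol 9.6.7 runs "through 30 days after the last dose of pegloticase and/or MTX (whichever is later"). SAP 14.2 has the same end.

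**The concern.** The contact is the last point at which adverse events are collected, so its date should not precede the end of the period in which events are counted. Under the infusion-based wording it does precede it for completers, because they take MTX after their last infusion and the TEAE window follows the later drug. Events in the final days of the window would not be asked about, yet the TEAE tables would show them as absent.

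No other contact clearly covers those days. The Week 24 visit falls about 14 days after the last infusion, well before them. The 30-day call after the last MTX dose for women of childbearing potential is described as an ovulation check, and only that group receives it. The trial plans about 30 subjects at 10 to 15 sites, or 2 to 3 per site, so sites could read the text differently without this being noticed.

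**Working it through.** **Inputs**

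- Study days: SAP Table 8 gives target days 155, 162 and 169 for Weeks 22, 23 and 24. The rule 7 × week + 1 reproduces them: 7 × 22 + 1 = 155, 7 × 23 + 1 = 162, 7 × 24 + 1 = 169. For the extension, Week 46 is 7 × 46 + 1 = 323.
- Last infusion: Week 22 (Day 155), or Week 46 (Day 323) in the extension.
- MTX timing: weekly, 1 to 3 days before an infusion, or failing that at least 60 minutes before it on the same day (Protocol 9.1, 9.4.1.1).
- MTX after the last infusion: one further weekly dose (Synopsis, 9.1, 9.4.1.1). The Schedule's dosing row ends at Week 23, or Week 47 in the extension.

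**Week 24 completer**

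1. Infusion-based contact: 155 + 30 = Day 185.
2. If the MTX dose before the last infusion was taken *d* days earlier (*d* = 0, 1, 2 or 3), the next weekly dose falls on Day 155 − *d* + 7 = 162 − *d*, that is Day 159 to 162.
3. TEAE window ends at last MTX + 30: Day 189 to 192.
4. Gap: 189 − 185 = 4 days to 192 − 185 = 7 days.
5. Share of the full window, counted from Day 1: 4/189 = 2.1% to 7/192 = 3.6%.

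**Extension completer**

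The contact is at 323 + 30 = Day 353. The last MTX dose is on Day 327 to 330, so the window ends on Day 357 to 360. The gap is again 4 to 7 days, or 4/357 = 1.1% to 7/360 = 1.9% of the window.

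**Later-of-two anchor**

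The contact and the end of the window are the same day, so the nominal gap is 0.

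**Effect of the ±3-day visit window**

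- Infusion anchor: 4 − 3 = 1 day to 7 + 3 = 10 days.
- Later-of-two anchor: 0 to 3 days, the 3 arising if the contact is made at the early edge.

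**Conditional case**

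Protocol 9.5.8.6 also lists MTX administration at the Week 24 or 48 visit. Taken literally, the last MTX dose is on Day 169, the window ends on Day 199 and the gap is 199 − 185 = 14 days (14/199 = 7.0%). This conflicts with the single additional weekly dose and with the Schedule's Week 23 end of dosing. It is a separate inconsistency that must be reconciled on its own.

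**The case against.** The strongest reply is that the operative text already works. Protocol 9.5.8.7 is the section that tells sites how to make this contact, footnote 25 agrees with it, and the sentence under the Synopsis heading overrides the heading. All three use the same anchor as the TEAE window, and the design overviews refer the reader to the Schedule for detail. This largely stands, and it is why the point is minor. It does not remove the contradiction: no rule of precedence is stated, and the overviews in both documents reserve the MTX date for subjects who were never infused.

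Four stronger readings are tempting, and the documents do not support them:

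- *That the gap is 4 to 14 days.* The 14-day end needs the MTX administration listed in 9.5.8.6, which other sections contradict.
- *That 12% to 19% of the window is lost.* Those figures (4/34 = 11.8%, 7/37 = 18.9%) divide by the days after the last infusion only. TEAEs are summarised over the whole pegloticase period, where the share is about 2% to 4% for a Week 24 completer.
- *That TEAE and SAE counts are too low and differ by site.* This requires sites to follow the overview wording and events to occur in those days. The documents show neither. Infusion reactions as defined in Appendix 17.9 (within 24 hours of an infusion) cannot fall there.
- *That the 9.6.7 summary of events more than 30 days after the last dose breaks down under the infusion anchor.* For completers that interval is nominally empty under either anchor. It still has content for subjects who stop early and stay on trial to Week 24.

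The extension sentence in 9.3.3.1.1 is also weak evidence. It gives no day count from the infusion, and its section concerns early stopping, when MTX stops too.

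**Conclusion.** The contradiction is in current text and the consequence follows from the plan's own definitions: one of the two stated rules ends AE collection before the analysed window closes. For completers at a site that follows that rule, the nominal shortfall is 4 to 7 days. This assumes weekly MTX timed as planned, one dose after the last infusion, and a contact made on its target day. Where footnote 25 or 9.5.8.7 is followed, the nominal shortfall is zero. Any actual undercount is a possibility that the documents neither establish nor exclude. The point is minor: it bears on the completeness of late TEAE capture, not on the primary endpoint or the sample size.

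**What to change.** - Bring the Synopsis (Trial Design component 5 and the Duration of Treatment heading), the Schedule's 30-day column header, Protocol 9.1 and SAP 4 into agreement with the Synopsis sentence, footnote 25 and Protocol 9.5.8.7 on one stated anchor. The sponsor decides which anchor is kept.
- State in Protocol 9.3.3.1.1 the date from which the contact is counted for extension subjects.
- Define the end of AE/SAE collection so that it is no earlier than the end of the TEAE window in Protocol 9.6.7 and SAP 14.2, allowing for the early edge of the ±3-day window.
- Separately, reconcile the MTX administration listed in Protocol 9.5.8.6 with the Synopsis, Protocol 9.1 and 9.4.1.1, and the Schedule. This review takes no position on which is right.

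The cost is wording in the two documents and, at most, a phone or email contact moved by about a week.

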2.1 Schedule of Assessments

Trial Procedure/ Assessment	Screening ¹	MTX Run-in Period ²		Pegloticase + MTX Treatment Period ³ Day 1 through Week 24 EOT																	Optional Extension to Wk 48
				Week (± 3 d)																	
	Screening Visit	(-6 wks ± 3 d)	(-4 wks ± 3 d)	(-2 wks ± 3 d)	Day 1	Wk 2	Wk 4	Wk 6	Wk 8	Wk 10	Wk 12	Wk 14	Wk 16	Wk 18	Wk 20	Wk 21	End of Pegloticase Visit ⁴ (if applicable)	Wk 22	Wk 23	Wk 24/ EOT*	Wk 24 (± 3 d)
					Inf: 1	Inf: 2	Inf: 3	Inf: 4	Inf: 5	Inf: 6	Inf: 7	Inf: 8	Inf: 9	Inf: 10	Inf: 11	Within 2 wks following final infusion	Inf: 12			Inf: 13	
Informed consent	X																				
Enrollment					X																
Demographic data	X																				
Inclusion/exclusion criteria	X	X	X	X	X																
Medical/surgical history ⁵	X																				
Medication/substance use history ⁶	X																				
Chest x-ray	X																				
Physical examination ⁷	X			X	X	X	X	X	X	X	X	X	X	X	X	X	X	X	X	X	
Vital signs, height ⁸	X	X	X	X	X	X	X	X	X	X	X	X	X	X	X	X	X	X	X	X	
Weight ⁹	X				X												X		X	X	
Electrocardiogram ¹⁰	X																				
AE/SAE assessment ¹¹	X	X	X	X	X	X	X	X	X	X	X	X	X	X	X	X	X	X	X	X	

Trial Procedure/ Assessment	Screening ¹	MTX Run-in Period ²		Pegloticase + MTX Treatment Period ³ Day 1 through Week 24 EOT																		Optional Extension to Wk 48	
				Week (± 3 d)																			
	Screening Visit	(-6 wks ± 3 d)	(-4 wks ± 3 d)	(-2 wks ± 3 d)	Day 1	Wk 2	Wk 4	Wk 6	Wk 8	Wk 10	Wk 12	Wk 14	Wk 16	Wk 18	Wk 20	Wk 21	End of Pegloticase Visit ⁴ (if applicable)	Wk 22	Wk 23	Wk 24/ EOT*	Wk 24 (± 3 d)		
Concomitant medications	X	X	X	X	X	X	X	X	X	X	X	X	X	X	X	X	X	X	X	X	X	Inf: 13	
Document gout flares and intensity	X	X		X	X	X	X	X	X	X	X	X	X	X	X	X	X	X	X	X	X	Inf: 12	
CCI [REDACTED]		X			X			X			X			X		X		X		X		X	
HAQ-DI	X			X			X			X			X		X		X		X		X	X	
CCI [REDACTED]		X			X						X					X		X		X		X	
CCI [REDACTED]		X			X						X					X		X		X		X	
CCI [REDACTED]		X			X						X					X		X		X		X	
CCI [REDACTED]		X			X						X					X		X		X		X	
DECT ¹²		X									X					X		X		X		X	
MTX dosing calendar	X	X	X	X	X	X	X	X	X	X	X	X	X	X	X	X	X	X	X	X	X	X	
MTX dispensed ¹³	X	X	X	X	X	X	X	X	X	X	X	X	X	X	X	X	X	X*				X	
MTX dosing		Once weekly from Week -6 to Week 23 Visit, inclusive																					X
Folic acid Rx filled ¹⁴		Rx filled as needed																					X
Gout prophylaxis Rxs filled ¹⁵				Rxs filled as needed																			X

Trial Procedure/ Assessment	Screening ¹	MTX Run-in Period ²		Pegloticase + MTX Treatment Period ³ Day 1 through Week 24 EOT																			Optional Extension to Wk 48
				Week (± 3 d)																			
	Screening Visit	(-6 wks ± 3 d)	(-4 wks ± 3 d)	(-2 wks ± 3 d)	Day 1	Wk 2	Wk 4	Wk 6	Wk 8	Wk 10	Wk 12	Wk 14	Wk 16	Wk 18	Wk 20	Wk 21	End of Pegloticase Visit ⁴ (if applicable)	Wk 22	Wk 23	Wk 24/ EOT*	Wk 24 (± 3 d)		
IR prophylaxis Rxs filled ¹⁶					Inf: 1	Inf: 2	Inf: 3	Inf: 4	Inf: 5	Inf: 6	Inf: 7	Inf: 8	Inf: 9	Inf: 10	Inf: 11		Within 2 wks following final infusion	Inf: 12				Inf: 13	
MTX compliance/ reconciliation			X	X	X	X	X	X	X	X	X	X	X	X	X		X	X		X	X	X	X
IR prophylaxis ¹⁶ and compliance (Yes/No)					X	X	X	X	X	X	X	X	X	X	X				X				X
Folic acid compliance (Yes/No)			X	X	X	X	X	X	X	X	X	X	X	X	X		X	X		X	X	X	X
Gout flare prophylaxis compliance (Yes/No)					X	X	X	X	X	X	X	X	X	X	X		X	X		X		X	
Pegloticase infusion					X	X	X	X	X	X	X	X	X	X	X				X				X
CCI [REDACTED]					X	X		X			X							X	X		X	X	X
CCI [REDACTED]		X			X	X		X			X			X				X	X		X	X	X
Pre-infusion CCI [REDACTED] sampling					X								X							X		X	X
sUA ¹⁹	X	X		X	X	X	X	X	X	X	X	X	X	X	X		X	X	X	X	X	X	

Trial Procedure/ Assessment	Screening ¹	MTX Run-in Period ²		Pegloticase + MTX Treatment Period ³ Day 1 through Week 24 EOT																		Optional Extension to Wk 48
				Week (± 3 d)																		
	Screening Visit	(-6 wks ± 3 d)	(-4 wks ± 3 d)	(-2 wks ± 3 d)	Day 1	Wk 2	Wk 4	Wk 6	Wk 8	Wk 10	Wk 12	Wk 14	Wk 16	Wk 18	Wk 20	Wk 21	End of Pegloticase Visit ⁴ (if applicable)	Wk 22	Wk 23	Wk 24/ EOT*	Wk 24 (± 3 d)	
sUA ¹⁹ (central)/blood					Inf: 1	Inf: 2	Inf: 3	Inf: 4	Inf: 5	Inf: 6	Inf: 7	Inf: 8	Inf: 9	Inf: 10	Inf: 11		Within 2 wks following final infusion	Inf: 12			Inf: 13	
Hematology	X				X	X	X		X			X					X			X	X	
Clinical chemistry	X				X	X	X		X			X					X			X	X	
eGFR (calculated by the central laboratory)	X				X	X		X			X					X			X	X		
Urine albumin: creatinine ratio	X				X	X		X			X					X			X	X		
G6PD test ²¹	X																					
hs-CRP	X				X						X					X			X	X		
Additional samples for future analysis ²²		X			X						X					X			X	X		
Pregnancy test ²³	X	X	X	X	X	X	X	X	X	X	X	X	X	X	X	X	X	X	X	X	X	

Trial Procedure/ Assessment	Screening ¹	MTX Run-in Period ²		Pegloticase + MTX Treatment Period ³ Day 1 through Week 24 EOT																		Optional Extension to Wk 48
				Week (± 3 d)																		
	Screening Visit	(-6 wks ± 3 d)	(-4 wks ± 3 d)	(-2 wks ± 3 d)	Day 1	Wk 2	Wk 4	Wk 6	Wk 8	Wk 10	Wk 12	Wk 14	Wk 16	Wk 18	Wk 20	Wk 21	End of Pegloticase Visit ⁴ (if applicable)	Wk 22	Wk 23	Wk 24/ EOT*	Wk 24 (± 3 d)	
					Inf: 1	Inf: 2	Inf: 3	Inf: 4	Inf: 5	Inf: 6	Inf: 7	Inf: 8	Inf: 9	Inf: 10	Inf: 11		Within 2 wks following final infusion	Inf: 12			Inf: 13	
CCI [REDACTED]			X														X			X	X	

Table footnotes and abbreviations are presented on the last page.

	Optional Pegloticase + MTX Extension Period (Week 26 through Week 46)												Wk 48/ EOT/ET	30-Day Post- Treatment Follow-up Visit ²⁵	MTX Partner Pregnancy Follow-up
	Week (± 3 d)														
	Wk 26	Wk 28	Wk 30	Wk 32	Wk 34	Wk 36	Wk 38	Wk 40	Wk 42	Wk 44	Wk 46			~30 days after last pegloticase infusion or MTX dose (± 3 d)	~3 months after last MTX dose
Trial Procedure/ Assessment	Inf: 14	Inf: 15	Inf: 16	Inf: 17	Inf: 18	Inf: 19	Inf: 20	Inf: 21	Inf: 22	Inf: 23	Inf: 24				
Physical examination ⁷						X							X		
Vital signs ⁸	X	X	X	X	X	X	X	X	X	X	X				
Weight ⁹													X		
AE/SAE assessment ¹¹	X	X	X	X	X	X	X	X	X	X	X				
Concomitant medications	X	X	X	X	X	X	X	X	X	X	X				
Document gout flares and intensity	X	X	X	X	X	X	X	X	X	X	X				
CCI						X							X		
HAQ-DI						X							X		
CCI						X							X		
CCI						X							X		
CCI						X							X		
CCI						X							X		
DECT ¹²													X		
MTX dosing calendar	X	X	X	X	X	X	X	X	X	X	X				
MTX dispensed ¹³	X	X	X	X	X	X	X	X	X	X	X				
MTX dosing	Once weekly from Week 24 to the Week 47, inclusive														

	Optional Pegloticase + MTX Extension Period (Week 26 through Week 46)												Wk 48/ EOT/ET	30-Day Post- Treatment Follow-up Visit ²⁵	MTX Partner Pregnancy Follow-up
	Week (± 3 d)														
	Wk 26	Wk 28	Wk 30	Wk 32	Wk 34	Wk 36	Wk 38	Wk 40	Wk 42	Wk 44	Wk 46			~30 days after last pegloticase infusion or MTX dose (± 3 d)	~3 months after last MTX dose
Trial Procedure/ Assessment	Inf: 14	Inf: 15	Inf: 16	Inf: 17	Inf: 18	Inf: 19	Inf: 20	Inf: 21	Inf: 22	Inf: 23	Inf: 24				
Folic acid Rx filled ¹⁴	Rx filled as needed														
Optional gout prophylaxis Rx filled if needed ¹⁵	Rx filled as needed														
IR prophylaxis Rx filled ¹⁶	Rx filled as needed														
MTX compliance/ reconciliation	X	X	X	X	X	X	X	X	X	X	X	X			
IR prophylaxis ¹⁶ and compliance (Yes/No)	X	X	X	X	X	X	X	X	X	X	X				
Folic acid compliance (Yes/No)	X	X	X	X	X	X	X	X	X	X	X	X			
Optional gout flare prophylaxis compliance (N/A, Yes/No)	X	X	X	X	X	X	X	X	X	X	X	X			
Pegloticase infusion	X	X	X	X	X	X	X	X	X	X	X				
CCI						X						X			
CCI						X						X			
Pre-infusion CCI sampling						X						X			
sUA ¹⁹	X	X	X	X	X	X	X	X	X	X	X				
Hematology						X						X			

	Optional Pegloticase + MTX Extension Period (Week 26 through Week 46)												Wk 48/ EOT/ET	30-Day Post- Treatment Follow-up Visit ²⁵	MTX Partner Pregnancy Follow-up
	Week (±3 d)														
	Wk 26	Wk 28	Wk 30	Wk 32	Wk 34	Wk 36	Wk 38	Wk 40	Wk 42	Wk 44	Wk 46			~30 days after last pegloticase infusion or MTX dose (±3 d)	~3 months after last MTX dose
Trial Procedure/ Assessment	Inf: 14	Inf: 15	Inf: 16	Inf: 17	Inf: 18	Inf: 19	Inf: 20	Inf: 21	Inf: 22	Inf: 23	Inf: 24				
Clinical chemistry						X							X		
eGFR (calculated by the central laboratory)						X							X		
Urine albumin: creatinine ratio						X							X		
hs-CRP						X							X		
Additional samples for future analysis ²²						X							X		
Pregnancy test ²³	X	X	X	X	X	X	X	X	X	X	X		X		X
CC1						X							X		
Partner pregnancy ²⁶															X

AE = adverse event; d = day(s); DECT = dual-energy computed tomography; eGFR = estimated glomerular filtration rate; CC1

ET = early termination; EOT = End of Trial; G6PD = glucose-6-phosphate dehydrogenase; HAQ-DI = Health Assessment Questionnaire-Disability Index; hs-CRP = high-sensitivity C-reactive protein; Inf = infusion; IR = infusion reaction; IV = intravenous; MTX = methotrexate; N/A = not applicable; NSAID = nonsteroidal anti-inflammatory drug.

PK = pharmacokinetic; CC1

CC1 sUA = serum uric acid; UA = uric acid; V= Visit; Wk(s) = Week(s).

NOTE: Unless stated otherwise, all procedures will be completed prior to pegloticase infusion.

* Week 24 is the final visit of the Pegloticase + MTX Treatment Period; trial drug is not administered for subjects who may not gain further benefit beyond 12 infusions based on the Principal Investigator's judgement.

Footnotes:

1. The Screening Visit can occur up to 42 days prior to the first dose of MTX at Week -6.

2. During the MTX Run-in Period, subjects with eGFR ≥ 45 mL/min/1.73 m² will inject SC MTX weekly at a starting dose of 15 mg at Weeks -6 and Week -5 increasing to 25 mg at Week -4 and continuing weekly throughout the trial. Subjects with eGFR ≥ 30 and < 45 mL/min/1.73 m² will inject SC MTX at a starting dose of 10 mg at Week -6 and Week -5 increasing to 15 mg at Week -4 and continuing weekly throughout the trial; subjects unable to tolerate the 15 mg dose of MTX will be considered MTX Run-in Screen Failures. If a subject becomes unable to tolerate MTX at 25 mg doses, the folic acid dose may be increased from 1 to 2 mg/day and/or the MTX dosage may be decreased to 20 or 15 mg, but to no less than 15 mg. Subjects who are unable to tolerate MTX at a minimum dose of 15 mg during the Run-in Period regardless eGFR will be considered MTX Run-in Screen Failures.
3. Subjects will be enrolled at the Day 1 Visit to receive pegloticase 8 mg IV every 2 weeks from Day 1 through Week 22, inclusive. During this 24-week Pegloticase + MTX Treatment Period, subjects who meet the Individual Subject sUA Discontinuation Criteria or discontinue treatment for another reason will remain in the trial for biweekly visits, including the Week 24/End of Trial/ET and 30-Day Post-Treatment Follow-up Visits.
4. Prior to Week 22, subjects who end treatment due to sUA level or other reasons should complete the End of Pegloticase Visit within 2 weeks of the last infusion and continue with trial procedures without infusion. Subjects will also complete all regularly scheduled Follow-up Visits, including the 30-Day Post-Treatment Follow-up email/phone call and Week 24/End of Trial/ET Visits.
5. The Investigator or designee will collect a complete gout history, other relevant medical/surgical history.
6. Medication history (i.e., prior medications) will include gout medications, starting at the time of diagnosis and up to screening visit, substance use history and all other medications up to the screening visit. Prior medications (not including gout medications and pegloticase) will be collected for 1 year prior to the screening visit. Detailed pegloticase use history, including reason for discontinuation and associated reactions, if any, will be collected.
7. A complete physical examination, including assessment of head, eyes, ears, nose and throat; heart; lungs; abdomen; skin; extremities; neurological status and musculoskeletal system, including an assessment for the presence of **CCI** as well as gout history and symptom severity, will be performed at the Screening Visit. A targeted physical examination per Investigator judgement will be conducted at all other indicated time points. On days when pegloticase is administered, the examination is conducted prior to pegloticase administration. At a minimum, the targeted physical examination should include assessment of heart, lungs and abdomen. Clinically significant findings from the targeted physical examinations will be recorded as AEs.
8. Routine vital signs, including blood pressure, respiratory rate, temperature and heart rate, will be measured. Heart rate and blood pressure measurements should be taken after the subject has been in a sitting position in a rested and calm state with proper positioning, including back support and feet flat on the floor, for at least 5 minutes. The subject's arm should be supported at heart level and the cuff placed on the bare arm. A large cuff should be used as needed to fit the upper arm and a consistent arm is to be used at each trial visit. The Korotkoff phase V will be used to determine diastolic blood pressure. During the Pegloticase + MTX Treatment Period visits, vital signs should be taken before the pegloticase infusion and any time after the end of the infusion, but prior to subject's discharge/release from the site. Height will be collected at the Screening Visit only.
9. Weight should be measured in kilograms or pounds when the subject is not wearing shoes. On days when pegloticase is administered, weight should be recorded prior to pegloticase administration.
10. Electrocardiogram should be completed during Screening and will be read at the site. When possible, a 12-lead electrocardiogram will also be performed at the time when a select AE of special interest (IR, anaphylaxis and major adverse cardiovascular event, defined as non-fatal stroke, non-fatal myocardial infarction, cardiovascular death and congestive heart failure) is suspected.
11. AEs/SAEs will be collected from the signing of the informed consent form until the 30-Day Post-Treatment Follow-up Visit. For each AE, the Investigator will be asked to record if the event was possibly an IR or anaphylaxis and if so, will be prompted to complete additional electronic case report forms. Females of childbearing potential will be asked to confirm if ovulation has occurred since the last dose of MTX. If the subject had not ovulated, a urine pregnancy test will be required.
12. The initial DECT scan will be performed after the Screening Visit, during the MTX Run-in Period and prior to the Day 1 Visit. Subsequent DECT scans may be performed ± 10 days from the scheduled visit date. Subjects who end pegloticase infusions prior to Week 24 should follow the scheduled time points and have a DECT scan at the End of Pegloticase (if applicable) and Week 24/End of Trial/ET Visits (detailed guidance is provided within the Imaging Manual). DECT will be carried out for all subjects where the site has the capability to conduct the test.
13. MTX will be dispensed and brought back to check compliance at each infusion visit. MTX should be injected 1 to 3 days prior to each pegloticase infusion; however, if a subject does not do so, MTX must be injected ≥ 60 minutes prior to each pegloticase infusion.

14. Subjects will take folic acid at a starting dose of 1 mg orally every day beginning Week -6 (preferably 2 days prior to the first dose of MTX) continuing until prior to the End of Pegloticase (if applicable) or until 1 week after the last pegloticase infusion for subjects who have not stopped pegloticase treatment. The folic acid dose can be increased or an alternative folate supplement can be used (see [Section 9.4.6.3.2.2](#) for detailed instructions).
15. Before a subject begins the Pegloticase + MTX Treatment Period, he or she must have been taking at least 1 standard gout flare prophylaxis regimen (i.e., colchicine and/or NSAIDs and/or low-dose prednisone \leq 10 mg/day) per protocol for \geq 1 week before the first dose of pegloticase and continue flare prophylaxis for at least 6 months per American College of Rheumatology guidelines ([FitzGerald et al, 2020](#)). Gout flare prophylaxis from Week 26 to the end of the trial will be administered, if needed, at the discretion of the Principal Investigator.
16. IR prophylaxis includes fexofenadine (180 mg orally) and prednisone (50 mg orally) administered the night before each infusion; fexofenadine (180 mg orally), famotidine (20 mg orally), montelukast (10 mg orally) and acetaminophen (1000 mg orally) administered on the morning of each pegloticase infusion and methylprednisolone (125 mg IV) over an infusion duration between 10 and 30 minutes, prior to each pegloticase infusion.
17. **CCI**
[REDACTED]
18. Serum samples for evaluation of **CCI** [REDACTED] will be collected prior to the first dose of MTX at Week -6, prior to pegloticase infusion on Day 1 and at Weeks 2, 6, 14, 22 and 36; and at the non-infusion End of Pegloticase (if applicable) or the Week 24 or 48/End of Trial/ET Visit. In the event of an AE suspected to be an IR, a serum sample will be collected at that time or at the subsequent visit for evaluation of pegloticase antibodies.
